8.13 Post-Study Adverse Events and Serious Adverse Events

The Investigator should report any death or SAE occurring at any time after a subject has completed or terminated a clinical trial, when such death or SAE may reasonably be related to the study therapy used in an investigational trial. Investigators are not obligated to actively seek AEs from former study participants.

8.14 Regulatory Aspects of Adverse Event Reporting

The Investigator will promptly report all SAEs within the timeframes specified in Section 8.13. Prompt notification of SAEs by the Investigator is essential so that UMMSM can meet legal obligations and fulfill ethical responsibilities towards the safety of all subjects participating in UMMSM-sponsored investigational trials.

The Investigator will comply with the applicable local regulatory requirements related to reporting of SAEs to his or her Institutional Review Board (IRB) or Independent Ethics Committee (IEC).

This protocol has been filed under an Investigational New Drug (IND) application with the FDA. A given SAE may qualify as an Expedited Safety Report (ESR) if the SAE is both at least possibly attributable to study therapy and unexpected. In this case, all Investigators participating in an IND study will receive an ESR.

The ESRs are prepared according to UMMSM policy and are forwarded to the Investigator as necessary. The purpose of the ESR is to fulfill specific regulatory and Good Clinical Practice (GCP) requirements regarding the product under investigation.

Based on previous trials involving intravenous infusion of allogeneic human MSCs, no AEs have been attributed to treatment administration; therefore, all AEs will be considered and documented as unexpected AEs.

All AEs occurring at any time during the trial will be collected, documented, and reported by the investigator. For each AE, the investigator will provide the date of onset and resolution, intensity, treatment required, outcome, seriousness, and potential causality with regards to the study exposure.

9. STATISTICAL ANALYSIS

9.1 Determination of Sample Size and Analysis Population

No formal statistical justification was performed to determine sample size in the Phase I study. Cohort size was determined based on expected requirements for safety analyses and projected enrollment rates. Study participants will be randomized according to a fixed allocation permuted block randomization schema. The allocation ratio will be 1:1:1:1 and the block size will be 4. All enrolled subject who received at least one treatment dose will be included in summaries of baseline characteristics, safety, and efficacy. Reasons for study discontinuation will be tabulated.

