Three (3) subjects will be treated with a single administration of 2×10^7 (20 million) UCMSCs delivered via peripheral intravenous infusion.

Group 2 (3 subjects)

Three (3) subjects will be treated with a single IV administration of 2×10^7 (20 million) BMMSCs delivered via peripheral intravenous infusion.

The subjects in the high dose (Groups 3 & 4) will not be treated until the subjects in the low dose (Groups 1 & 2) have completed their one-month follow-up assessments and safety measures have been reviewed to confirm that there have been no treatment emergent SAE's.

Group 3 (3 subjects)

Three (3) subjects will be treated with a single IV administration of 1×10^8 (100 million) UCMSCs delivered via peripheral intravenous infusion.

Group 4 (3 subjects)

Three (3) subjects will be treated with a single IV administration of 1×10^8 (100 million) BMMSCs delivered via peripheral intravenous infusion.

Randomized Phase (30 subjects)

Group A (10 subjects – UCMSCs)

Ten (10) subjects will be treated with a single administration of 1×10^8 (100 million) UCMSCs delivered via peripheral intravenous infusion.

Group B (10 subjects – BMMSCs)

Ten (10) subjects will be treated with a single administration of 1×10^8 (100 million) BMMSC delivered via peripheral intravenous infusion.

Group C (10 subjects – Placebo)

Ten (10) subjects will be treated with a single administration of placebo delivered via peripheral intravenous infusion.

Subjects in each pilot phase group (Group 1, 2, 3 and 4) will not be treated less than 5 days apart.

The randomized portion of the study will be conducted after a full review of the safety data from the Pilot Phase by the DSMB

Patients will be randomized in a 1:1:1:1 ratio to one of the 3 groups in the randomized phase. For subjects randomized to B (BMMSCs); the cells will be derived from a healthy allogeneic bone marrow donor (obtained by iliac crest aspiration).

For subjects randomized to Group A (UCMSCs); the cells will be derived from a healthy allogeneic umbilical cord tissue donor.

Route of Administration	Peripheral Intravenous Infusion
Duration of Study Participation	12 months (Follow-up will be at 2 weeks, 1 Month, 3, 6, and 12 months.)
Inclusion Criteria	
1. Provide written informed consent2. Subjects age ≥ 21 and ≤ 95 years at the time of signing the Informed Consent Form.3. Each subject must have endothelial dysfunction. Endothelial dysfunction Criteria:

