3. STUDY DESIGN

3.1 Description of the Study

A Pilot Phase will be performed to test the safety of dose and volume of cells administered via peripheral intravenous infusion. The first three (3) subjects in-group 1 (UCMSCs) will be treated first and safety will be fully assessed. Only if there is no evidence of treatment emergent SAEs in Group 1, treatment of subjects in Group 3 be undertaken.

The subjects in the high dose (Groups 3 & 4) will not be treated until the subjects in the low dose (Groups 1 & 2) have completed their one-month follow-up assessments and safety measures have been reviewed to confirm that there have been no treatment emergent SAE's. Treatment emergent SAE's, defined as the composite of: death, non-fatal pulmonary embolism, stroke, hospitalization for worsening dyspnea and clinically significant laboratory test abnormalities, prior to proceeding with the treatment of further subjects.

Subjects in each pilot phase group (Group 1, 2, 3 and 4) will not be treated less than 5 days apart.

Subjects in the pilot phase will receive a telephone call 5 days post infusion (+/- 1 day) to review adverse events.

The randomized portion of the study will be conducted after a full review of the safety data from the Pilot Phase by the DSMB.

Following the pilot study (12 subjects), thirty (30) subjects that meet inclusion criteria will be scheduled to undergo peripheral intravenous infusion.

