4.4 Withdrawal Criteria

Subjects will be informed that they have the right to withdraw from the study at any time and for any reason without prejudice to future or continued medical care. Subjects must be withdrawn for the following reasons:

- Subject request.
- Subject is unable or unwilling to comply with the protocol.
- Medical reasons, at the discretion of the investigator.

Reason for withdrawal will be recorded in the subject's case report form. In order to adequately monitor for safety and potential efficacy outcomes, subjects who are withdrawn for any reason after receiving the first infusion should be encouraged to return for all assessments through the end of the study period. All efforts should be made to continue to record safety data and lung function parameters for all withdrawn subjects. Subjects who withdraw for reasons unrelated to the study or study drug (e.g. withdrawal of consent or loss to follow-up) may be replaced if deemed necessary to meet study objectives. Replacement subjects will be assigned unique identification numbers.

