9.3 Interim Analyses

Interim analyses will be conducted at times coincident with regularly scheduled meetings of the Data and Safety Monitoring Board (DSMB) at approximately six-month intervals. The DSMB Chair will be notified each time an SAE occurs. After all subjects in phase I have been followed for 30 days, at that time an independent DSMB will review all available data to make an independent recommendation to either keep the specified randomized dose 1:1:1 or to recommend a dose modification for the randomized placebo study.

Policies of the DSMB will be described in the DSMB Charter, which will be prepared by the DSMB prior to study initiation. The stopping guidelines serve as a trigger for consultation with the DSMB for additional review, and are not formal “stopping rules” that would mandate automatic closure of study enrollment.

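### The randomisation rule (1:1:1:1 in blocks of 4) cannot be run in a three-arm phase of 30 subjects and contradicts both the planned 10/10/10 and the 1:1:1 in Section 9.3

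*Combined protocol and SAP*

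**What the plan says.** Section 9.1 (Determination of Sample Size and Analysis Population) describes the method: "Study participants will be randomized according to a fixed allocation permuted block randomization schema". It then fixes the parameters: "The allocation ratio will be 1:1:1:1 and the block size will be 4".

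The synopsis (Design and Investigational Plan) repeats the ratio and ties it to the randomised phase: "Patients will be randomized in a 1:1:1:1 ratio to one of the 3 groups in the randomized phase". It lists three randomised groups: A (UCMSCs), B (BMMSCs) and C (placebo), each of 10. For Group C it says: "Ten (10) subjects will be treated with a single administration of placebo delivered via peripheral intravenous infusion". Section 3.1 gives the same total: after the pilot, "thirty (30) subjects that meet inclusion criteria will be scheduled to undergo peripheral intravenous infusion". Section 3.2 also names three treatments.

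Section 9.3 (Interim Analyses) describes the DSMB's choice after the pilot as either to "keep the specified randomized dose 1:1:1" or to recommend a dose modification. Section 6.6 (Blinding and Un-blinding) mentions randomisation but gives no ratio or block size. No section describes a fourth randomised arm or says what a fourth slot would be for.

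**The concern.** The synopsis sentence contradicts itself, with four ratio terms for three groups. Section 9.1 carries the same error into the block size. Correcting the ratio alone would leave 1:1:1 in blocks of 4, which is still impossible. Section 9.1 is the only place that gives a block size, so the reader cannot look up the right one.

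Two things are at stake. First, the allocation list cannot be produced from the text. Someone must choose a workaround that the protocol does not document, and the plausible choices give different arm sizes. Second, conduct will differ from the protocol whatever is done: a list that guarantees 10/10/10 departs from Section 9.1, and a list that follows Section 9.1 misses 10/10/10. The primary objective is to compare the safety of two cell products, and the allocation rule is what makes that comparison a randomised one.

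**Working it through.** **Inputs.** Randomised total 30 and three arms of 10 (synopsis; the total is also in Section 3.1). Ratio 1:1:1:1 (synopsis and Section 9.1). Block size 4 (Section 9.1). Ratio 1:1:1 (Section 9.3).

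**Can the rule give the planned 10/10/10?**
- Blocks needed: 30/4 = 7.5, that is 7 full blocks plus 2 subjects.
- Equal shares of a block of 4 over three arms: 4/3 = 1.33 subjects per arm, which is impossible. The only whole-number splits using all three arms are 2:1:1 and its permutations.
- Expected number per label with four labels: 30/4 = 7.5, not 10.
- By contrast, 1:1:1 gives 30/3 = 10 per arm, which matches the plan.

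**What each way of handling the fourth label produces.** Precision is the standard error (SE) of a difference between two arm means relative to 10 v 10, assuming equal SDs: ratio = √[(1/a + 1/b)/(2/10)]. The documents specify none of these four workings.

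1. *Taken literally, with four labels.* Seven full blocks plus 2 subjects give 7, 7, 8 and 8, so 7 or 8 of the 30 draw a label with no treatment. If they were lost, the SE ratios among the three real arms would be √(0.2500/0.2) = 1.118 for 8 v 8, √(0.2679/0.2) = 1.157 for 7 v 8, and √(0.2857/0.2) = 1.195 for 7 v 7.

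2. *Fourth label folded into one arm (2:1:1).* Seven blocks give 14:7:7, and the last 2 subjects bring this to 14:8:8, 15:7:8 or 16:7:7. Comparisons with the enlarged arm keep about the planned SE: 14 v 8 = 0.991, 15 v 7 = 1.024, 15 v 8 = 0.979, 16 v 7 = 1.013. The two smaller arms compare with ratios of 1.118 to 1.195, that is 12–20% worse.

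3. *Spare slot in each block given to a random arm.* After 7 blocks each arm has 7 plus its share of 7 random extras (3⁷ = 2187 equally likely sequences). The first 2 places of block 8 are one particular pair of different arms with probability 5/18, or both in one particular arm with probability 1/18. To end at 10/10/10:
   - with a mixed pair, the extras must split 2, 2, 3: 7!/(2!2!3!) = 210 ways;
   - with a same-arm pair, they must split 1, 3, 3: 7!/(1!3!3!) = 140 ways.

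   The probability is [3 × (5/18) × 210 + 3 × (1/18) × 140]/2187 = 198.33/2187 = 595/6561 = 9.1%. The same enumeration gives 2625/6561 for 9/10/11 in any order and 756/6561 for 9/9/12 in any order. The smallest arm is therefore 8 or fewer with probability 1 − (595 + 2625 + 756)/6561 = 2585/6561 = 39.4%.

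4. *Fourth label left unused.* Ten blocks × 3 used labels = 30, giving 10/10/10. This is really 1:1:1 in blocks of 3, not the written rule.

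**Could the rule belong to the pilot?** The pilot has four groups of 3, and 12/4 = 3 blocks would give 3/3/3/3. The synopsis, however, ties the ratio to the randomised phase. Groups 3 and 4 also wait until Groups 1 and 2 have completed one-month follow-up, so the four pilot groups cannot be filled from common blocks.

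**Which block sizes work?** Multiples of 3 that divide 30 are 3, 6, 15 and 30. Block 3 gives ten blocks and block 6 gives five; both yield exactly 10/10/10. Blocks of 9 or 12 do not divide 30 (3.33 and 2.5 blocks).

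**The case against.** The case for treating this as editorial is fair in several respects. The arm sizes are stated independently of the ratio, and Section 9.3 shows that 1:1:1 was meant. Folding the fourth label into one arm would contradict the stated 10 per arm. Of the three workarounds (items 2–4 above), only leaving the label unused guarantees 10/10/10, and it costs nothing. The literal outcome in item 1 is an outer bound: a label with no product would probably be noticed when the list is built or first used. Missing 10/10/10 also does little harm to precision in item 3. For example, 8 v 11 raises the SE by 3.9% (√1.0795), and 9 v 10 by 2.7% (√1.0556). The match between blocks of 4 and the four pilot groups suggests leftover drafting.

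All of that stands as to size. It does not remove the error. The harmless workaround is itself a departure from Section 9.1, nothing in the documents selects it, and the only stated block size is wrong for three arms.

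On the remedy, a block size that divides 30 is stricter than strictly needed, since a truncated last block would unbalance the arms only slightly. It is harmless, however, and it guarantees the stated arm sizes. There is also a fair point about prediction: with a small fixed block printed in the protocol of a single-centre trial, the last assignment in a block can be deduced if the others become known.

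**Conclusion.** The concern holds. As written, the rule cannot deliver 10/10/10 in the three-arm phase, it conflicts with Section 9.3, and the block size cannot be recovered from any other section. It needs correcting because it is an operative instruction, not because a large loss has been shown.

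The size of the consequence depends on an unstated choice. It ranges from nothing (fourth label unused), through a 12–20% larger SE for one of the three comparisons (label folded into one arm), to a 12–20% larger SE for every comparison in the unlikely literal case. These ratios assume equal SDs across arms. No stated power is affected: Section 9.1 gives no formal basis for the sample size, and Section 9.2 calls efficacy exploratory.

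**What to change.** In the synopsis and in Section 9.1, state that the randomised phase allocates 1:1:1 to Groups A, B and C, 10 per arm, in permuted blocks whose size is a multiple of 3 and divides 30. Ten blocks of 3 or five of 6 would do. Mixed sizes also work if constrained to total 30, for example four of 3 and three of 6 (12 + 18 = 30). To limit prediction, the exact sizes can be kept in a restricted randomisation specification, with the protocol stating only the ratio and the constraint.

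Append spare blocks to the list, because Section 4.4 says that subjects who withdraw for unrelated reasons "may be replaced if deemed necessary to meet study objectives". If a list already exists, record how it was generated and how the fourth label was handled.

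The cost is a short correction in two places and generation of the list. No extra patients are needed, and Sections 3.1 and 9.3 already agree with the corrected text.

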9.2 General Statistical Methods

All statistical tests will be performed at an $\alpha=0.05$ level of significance, using two-sided tests. Because this is a Phase I study with only exploratory efficacy outcomes, no adjustments will be made for multiple analyses. Continuous variables will be presented by descriptive statistics. Categorical variables will be presented by counts. Two sided 95% confidence intervals will be calculated and presented where appropriate.

Analysis of AEs will include tabulation by frequency, severity, organ system affected, and relationship to study exposure. Lung function data will be summarized descriptively. Subject reported outcome data will be summarized according to the guidelines of each questionnaire.

9.3 Interim Analyses

Interim analyses will be conducted at times coincident with regularly scheduled meetings of the Data and Safety Monitoring Board (DSMB) at approximately six-month intervals. The DSMB Chair will be notified each time an SAE occurs. After all subjects in phase I have been followed for 30 days, at that time an independent DSMB will review all available data to make an independent recommendation to either keep the specified randomized dose 1:1:1 or to recommend a dose modification for the randomized placebo study.

Policies of the DSMB will be described in the DSMB Charter, which will be prepared by the DSMB prior to study initiation. The stopping guidelines serve as a trigger for consultation with the DSMB for additional review, and are not formal “stopping rules” that would mandate automatic closure of study enrollment.

9.4 Data Safety Monitoring Board (DSMB)

9.4.1. ROLE OF THE DSMB

This study is designed to test the safety of the study investigational product in subjects with chronic inflammation due to metabolic syndrome.

The purpose of the data safety monitoring board (DSMB) is to advise the investigators regarding the continuing safety of study patients and those yet to be recruited to the study, as well as the continuing validity and scientific merit of the study.

This section describes the roles, responsibilities and operating procedures of the DSMB, and includes guidelines for communications and interactions between the DSMB and the investigators to schedule and format for meetings; format for presentation of data; specification of who will have access to interim data and who may attend all or part of DSMB meetings; procedures for assessing conflict of interest of potential DSMB members; and the method and timing of providing interim reports to the DSMB.

9.4.2. Purpose of the DSMB

The primary function of the DSMB is to review the accumulating unblinded safety data from each study group and using the data as the basis for recommendations concerning the continuation and/or modification of the study. This will be accomplished through regularly scheduled formal meetings and/or additional meetings to review interim summaries of safety and efficacy data. The DSMB will make recommendations regarding modification or termination of the study in the event of significant study conduct issues or safety concerns. The DSMB will not stop the study based on efficacy results favorable to hMSCs, other than for all-cause mortality as outlined below. The selected primary and secondary endpoints were chosen to measure major morbidity in subjects with chronic inflammation due to metabolic syndrome. Given the importance of mortality in patients with metabolic syndrome who are at high risk for cardiovascular disease, a stopping boundary based on the all-cause mortality rate will be implemented to guide the DSMB.

9.4.2.1 DSMB MEMBERSHIP

The DSMB is an independent, multidisciplinary group consisting of four members (inclusive of the DSMB chair). The members include a clinical trialist, a biostatistician, an expert gerontologist and an expert cardiologist.

The DSMB will meet until the study's database has been locked and a final data review has been completed. If a member withdraws from the DSMB, the DSMB chairperson will be responsible for selecting an appropriate replacement.

9.4.2.2 Financial Disclosure and Conflict of Interest

DSMB membership is restricted to individuals without significant potential or perceived conflicts of interest. The source of these conflicts may be financial, scientific, or regulatory in nature.

Members must disclose to the DSMB chairperson their consultancies (direct or indirect) in excess of \$5,000 or financial interests in any pharmaceutical companies, biotechnology companies, or CROs, if these relationships could lead to any conflict of interest or these companies' products involve hMSCs.

The DSMB chairperson will be responsible for deciding whether consultancies or financial interests of the members materially impact their objectivity. This decision is to be based on the reasonable belief that their objectivity is not in doubt. DSMB members will be responsible for advising the DSMB chairperson of any changes in financial interests in pharmaceutical companies, biotechnology companies, including consultancies, during the course of their membership. Members of the DSMB who develop significant potential or perceived conflicts of interest that may materially impact their objectivity will be asked to resign from the DSMB.

9.4.2.3 DSMB Responsibilities

The DSMB has the responsibility to:

1. Review the protocol and all amendments. The DSMB will also be provided the Investigator's Brochure, as it is updated, that includes preclinical and clinical efficacy and safety data.
2. Review the statistical analysis plan with particular attention to the portions describing the data to be provided to the DSMB.
3. Review Periodic Safety Update Reports (PSURs).
4. Evaluate the conduct of the study including the selection and retention of subjects, extent of protocol deviations, treatment adherence, and the quality of the data. The DSMB shall make recommendations regarding study conduct as necessary to protect the scientific

integrity of the study. The DSMB shall not make recommendations regarding the efficacy outcomes or associated analyses.

5. Review unblinded periodic safety summaries including adverse events, serious adverse events, discontinuations, and post-baseline laboratory results. In addition, efficacy and mortality data will be reviewed, although the DSMB shall not recommend stopping the study for efficacy.

6. Evaluate the conduct of the study including enrollment rates, the selection and retention of patients, protocol deviations, treatment adherence and quality and completeness of the data

7. The DSMB will make recommendations regarding modification or termination of the study in the event that significant safety concerns arise during study conduct.

